11.1. General Notes Regarding Dose Modification

When several toxicities with different grades of severity occur at the same time, the dose modifications should be according to the highest grade observed.

The investigator may use discretion in modifying or accelerating the dose modification guidelines depending on the severity of toxicity and an assessment of the risk versus benefit for the patient, with the goal of maximizing patient compliance and access to supportive care.

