In general, blood transfusions and erythroid growth factors are permitted as clinically indicated.

Abbreviation: CBC: complete blood count, TSH: thyroid stimulating hormone, LDH: lactate dehydrogenase

Management of Mucosal/Non-tumor and Tumor Bleeding

| Mucosal Bleeding | |
|--|--|
| 
Events of mild to moderate severity are a potential risk for binrafusp alfa.In general, these reactions resolve without discontinuation of treatment.Events may include, but are not limited to the following:
EpistaxisHemoptysisGingival bleedingHematuria | |
| Mucosal/Non-tumor Bleeding | |
| Grading | Management |
| Grade 2 | 
If resolves to Grade ≤ 1 by the day before the next infusion, study intervention may be continuedIf not resolved to Grade ≤ 1 by the day before the next infusion, but is manageable and /or not clinically relevant, consult Medical Monitor to assess if clinically reasonable to administer the following infusion. |
| Grade ≥ 3 | 
Permanently discontinue treatment unless an alternative explanation can be identified (such as concomitant use of antithrombotic agents, traumatic events, etc.)In case of alternative explanations, hold study treatment until the event recovers to Grade ≤ 1If Grade ≥ 3 bleeding event is observed, regardless of causality with the study intervention, upon resumption of study intervention binrafusp alfa dose should be reduced by 50% (600 mg Q2W. Once there is stable resolution and no recurrence of bleeding on reduced dose, Investigator is encouraged to communicate with sponsor on potential dose re-escalation after careful benefit-risk assessment |
| Grade 4 | 
Treatment must be permanently discontinued if no alternative explanation is identified. |

| | |
|---|--|

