| 
In case of rapid decrease of hemoglobin (Hgb), such as a decrease greater than 2.0 g/dL across a 2 weeks period, withhold the subsequent cycles of study intervention until Hgb is stabilized and do a thorough assessment of bleeding (for example, upper and lower GI endoscopy, enhancement CT etc.); if Grade 1 or greater bleeding is observed or suspected, withhold the bintrafusp alfa until the bleeding is resolved/controlled and resume the dose of bintrafusp alfa reduced by 50%. Once Hgb decrease is recovered to \leq Grade 1 or baseline and stably controlled, the Investigator is encouraged to communicate with Medical Monitor to re-escalate the dose. The dose of bintrafusp alfa may be re-escalated to full dose once Hgb is stabilized without further need for blood transfusion in the subsequent cycles. The timing of re escalation may need a case-by-case decision. See Section Table on Management of anemia | |
| Tumor Bleeding | |
| Grade \geq 2 | 
Study treatment must be held till the event recovers to Grade \leq 1Permanently discontinue treatment if the Investigator considers the participant to be at risk for additional severe bleeding. |
| Grade \geq 3 | 
If Grade \geq 3 bleeding event had been observed, regardless of causality with the study intervention, upon resumption of the study intervention bintrafusp alfa dose should be reduced by 50%. Once there is stable resolution and no recurrence of bleeding on reduced dose, Investigator is encouraged to communicate with the sponsor potential dose re-escalation after careful benefit-risk assessment. Treatment should be permanently discontinued if the Investigator considers the participant to be at risk for additional severe bleeding.In case of rapid decrease of hemoglobin (Hgb), see Section Mucosal/Non-Tumor bleeding. |

Impaired Wound Healing

- Impaired wound healing is considered important potential risk for bintrafusp alfa
- Management should be discussed with Medical Monitor for participants requiring surgery on study.
- It is recommended to hold study intervention for approximately 4 weeks post major surgery for observation.
- Post-operative wound healing should be closely monitored

12. Prohibited and permitted concomitant treatments

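### Section 11.2: the rapid-haemoglobin-fall bullet directs resumption at half dose after any bleed of Grade 1 or higher, without excepting bleeds for which the same table requires a permanent stop (minor patient-safety wording conflict)

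*Combined protocol and SAP*

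**What the plan says.** All the text is in the combined protocol and SAP.

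- **Haemoglobin bullet (section 11.2, bleeding table).** The trigger is "In case of rapid decrease of hemoglobin (Hgb), such as a decrease greater than 2.0 g/dL across a 2 weeks period". Later cycles are withheld and bleeding is looked for. Then, "if Grade 1 or greater bleeding is observed or suspected", sites are to "withhold the bintrafusp alfa until the bleeding is resolved/controlled and resume the dose of bintrafusp alfa reduced by 50" percent. Further on: "The dose of bintrafusp alfa may be re-escalated to full dose once Hgb is stabilized without further need for blood transfusion". The bullet ends with a pointer: "See Section Table on Management of anemia".
- **Mucosal/non-tumor bleeding, Grade 3 or higher.** "Permanently discontinue treatment unless an alternative explanation can be identified". If there is an alternative explanation, treatment is held until recovery to Grade 1 or lower. A further bullet sets half dose (600 mg every two weeks) at the point of resumption.
- **Mucosal/non-tumor bleeding, Grade 4.** "Treatment must be permanently discontinued if no alternative explanation is identified".
- **Tumor bleeding.** Both the Grade 2-or-higher row and the Grade 3-or-higher row require a permanent stop if the investigator sees a risk of further severe bleeding. The Grade 3-or-higher row also sends rapid haemoglobin falls to the mucosal/non-tumor section, and so to the same bullet.
- **Section 11.1.** The highest-grade rule begins "When several toxicities with different grades of severity occur at the same time" and makes the highest grade govern. A second sentence gives the investigator discretion.

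**The concern.** The bullet covers bleeding from Grade 1 upward, and as worded that includes Grades 3 and 4. Its instruction to resume is direct. It does not mention an alternative explanation, and it is not limited to participants who are still allowed treatment. A severe bleed can plausibly cause a haemoglobin fall of more than 2.0 g/dL in two weeks, so one event can trigger both the bullet and a permanent-stop row.

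At stake is re-exposure, possibly up to full dose, after an unexplained severe bleed or after a tumor bleed judged likely to recur severely. In a multi-center trial a mandatory stop should not depend on each site working out for itself which instruction takes precedence. A monitor also could not tell from the text alone whether a resumption in such a case is a protocol deviation.

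**Working it through.** The plan has no figure to reproduce on this point. The check sets the rules side by side and then works out the doses.

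**1. Where the rules overlap, given a rapid haemoglobin fall**

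- Mucosal/non-tumor Grade 1 or 2: no permanent-stop rule applies, so there is no conflict.
- Mucosal/non-tumor Grade 3 or higher with an alternative explanation: the row itself leads to a hold and then 600 mg every two weeks, so the initial action agrees.
- Mucosal/non-tumor Grade 3 or 4, unexplained: the rows say stop permanently and the bullet says resume at half dose. **Conflict.**
- Tumor bleed of Grade 3 or higher, referred to the bullet, where the investigator sees a risk of further severe bleeding: the row says stop permanently and the bullet says resume at half dose. **Conflict.**

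Without the haemoglobin fall the bullet does not apply and nothing conflicts.

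**2. Does section 11.1 decide the conflict cases?** Its rule needs several toxicities, of different grades, at the same time.

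- Bleed graded higher than the haemoglobin fall: the bleed governs, so treatment stops. Settled.
- Equal grades: the condition of different grades is not met. Stopping is still the sensible result, because only the bleeding rows are keyed to a grade at that level, but the rule does not say so.
- Haemoglobin fall graded higher: the rule points away from the bleed. The anemia text lists tests and permits transfusion and growth factors, but has no hold, stop or resume rule. The bullet is not keyed to anemia grade either, so section 11.1 cannot be said to make the bullet prevail. It simply does not settle the case.
- The fall treated as part of a single bleeding event: there are not several toxicities. Not settled.

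**3. Does other text rank the rules?** The discretion sentence in section 11.1 and the medical-judgment wording in section 17.2 allow stopping but set no order. The bullet's pointer leads to the anemia text, which has no dosing rule. Neighbouring rows are drafted differently: in both the mucosal/non-tumor and the tumor rows for Grade 3 or higher, the 50% reduction is tied to the moment of resumption, which is compatible with a stop. In this bullet the resumption is itself the instruction.

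**4. Dose in the overlap.** Section 10.1 gives 1200 mg every 14 days, and a cycle is 28 days, so there are 28 / 14 = 2 infusions per cycle.

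- Permanent stop: 0 mg per cycle.
- Bullet, on resumption: 0.5 × 1200 = 600 mg per infusion; 2 × 600 = 1200 mg per cycle.
- Bullet, after re-escalation: 2 × 1200 = 2400 mg per cycle.

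These figures describe the gap between the instructions. They do not estimate harm.

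**The case against.** The strongest answer is that the table should be read as a whole. A permanent stop ends treatment, so a bullet about later cycles and resumption has no one left to apply to. The Grade 3-or-higher mucosal row already contains a half-dose rule that applies whatever the cause and does not restate the stop, and nobody would read that rule as cancelling it. The bullet's evident purpose is extra caution: to search for bleeding behind a haemoglobin fall and to add a hold from Grade 1, for which there is no row. Nothing suggests that it was meant to relax the mandatory Grade 4 wording.

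There are also safeguards. Section 13.2 (Note 3) treats a laboratory abnormality that interrupts the drug as an SAE, and section 13.5 requires reporting within 24 hours, so the sponsor should learn of such a case early. Section 11 requires the Trial Chair to be consulted when doses are omitted for more than 8 weeks. Re-escalation is optional, its timing is a case-by-case decision, and contact with the Medical Monitor is encouraged.

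Most of this stands. It makes stopping the natural reading and lowers the practical risk. It does not supply the missing precedence: the neighbouring half-dose rules are conditional on resumption, this one is not, and the safeguards give notice without saying which instruction is correct.

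A reader might infer that the protocol requires re-dosing after an unexplained life-threatening bleed. The documents do not support that: the Grade 4 stop is mandatory, section 11.1 favours it where the bleed has the higher grade, and investigator discretion remains. Nor is the table contradictory for every severe bleed, since explained Grade 3-or-higher mucosal bleeds may resume under their own row.

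**Conclusion.** The wording conflict is real and minor. Taken literally, the bullet directs resumption at half dose in two situations where the same table requires a permanent stop: unexplained mucosal/non-tumor bleeds of Grade 3 or higher, and tumor bleeds referred to the bullet where the investigator sees a risk of further severe bleeding. Section 11.1 resolves part of the overlap, and no text states the precedence for the rest.

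The conclusion rests on the bullet's literal wording. Whether it is printed as a row across the table or inside the Grade 4 cell could not be established from the extracted text, but the overlap in wording is the same either way. How often a rapid haemoglobin fall accompanies such a bleed is not given, so no number of affected participants can be stated. The point has no bearing on sample size, power, type I error or the primary analysis.

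**What to change.** In the haemoglobin bullet, between the withholding step and the resumption step, insert: *unless permanent discontinuation is required by the Mucosal/Non-tumor Bleeding rows (Grade ≥ 3 or Grade 4, unexplained) or by the Tumor Bleeding rows (further severe bleeding judged a risk)*. Leave the half-dose wording after it unchanged.

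Both sets of rows should be named. The tumor-bleeding rows have their own Grade 3-or-higher entry and send cases to this bullet, so an unspecified reference to the Grade 3 or Grade 4 row would be ambiguous and would leave out the tumor-bleeding stop rule. The re-escalation sentences then apply only to participants who were allowed to resume.

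The cost is one clause at the next amendment. It adds no patients, visits or tests.

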13.1. Definition of an Adverse Event (AE) and AE's reporting

The main criterion for tolerability is the occurrence of toxicities and Adverse Events (AEs). [REDACTED]

[REDACTED]

[REDACTED]

[REDACTED]

[REDACTED]

[REDACTED]

An adverse event can therefore be any of the following:

Any unfavorable and unintended sign (including an abnormal laboratory finding) (see **NOTE 1** below), symptom, or disease temporally associated with the use of a medicinal product, whether or not considered related to the medicinal product.

Any new disease or exacerbation of an existing disease (a worsening in the character, frequency, or severity of a known condition), except events that are clearly consistent with the expected pattern of the disease progression. These data will be captured as efficacy assessment data only. If there is any uncertainty as to whether an event is due to disease progression, it should be reported as an adverse event.

Recurrence of an intermittent medical condition (e.g., headache) not present at baseline.

Any deterioration in a laboratory value or other clinical test (e.g., ECG, X-ray) that is associated with symptoms or leads to a change in study treatment or concomitant treatment or discontinuation from study drug.

Adverse events that are related to a protocol-mandated intervention, including those that occur prior to assignment of study treatment (e.g., screening invasive procedures such as biopsies).

Adverse events that occur during or within 24 hours after study drug administration and are judged to be related to study drug infusion should be captured as a diagnosis (e.g., "infusion-related reaction" or "anaphylactic reaction") on the Adverse Event eCRF. If a patient experiences both a local and systemic reaction to the same dose of study drug, each reaction should be recorded separately on the Adverse Event eCRF. Associated signs and symptoms should be recorded on the dedicated Infusion-Related Reaction eCRF.

A pre-existing medical condition should be recorded as an adverse event only if the frequency, severity, or character of the condition worsens during the study (e.g., "more frequent headaches").

NOTE 1: Abnormal laboratory and vital signs values:

A laboratory test result must be reported as an adverse event if it is a change from baseline and meets any of the following criteria:

Is accompanied by clinical symptoms,

Results in a change in study treatment (e.g., dosage modification, treatment interruption, or treatment discontinuation),

Results in a medical intervention (e.g., potassium supplementation for hypokalemia) or a change in concomitant therapy,

Is clinically significant in the investigator's judgment.

If a clinically significant laboratory abnormality is not a sign of a disease or syndrome, the abnormality itself should be recorded on the Adverse Event eCRF, along with a descriptor indicating if the test result is above or below the normal range (e.g., "elevated potassium").

A vital sign result must be reported as an adverse event if it is a change from baseline and meets any of the following criteria:

Is accompanied by clinical symptoms,

Results in a change in study treatment (e.g., dosage modification, treatment interruption, or treatment discontinuation),

Results in a medical intervention or a change in concomitant therapy,

Is clinically significant in the investigator's judgment.

If a clinically significant vital sign abnormality is a sign of a disease or syndrome (e.g., high blood pressure), only the diagnosis (i.e., hypertension) should be recorded on the Adverse Event eCRF.

The finding of an elevated ALT or AST ($> 3 \times$ baseline value) in combination with either an elevated total bilirubin ($> 2 \times$ ULN) or clinical jaundice in the absence of cholestasis or other causes of hyperbilirubinemia is considered to be an indicator of severe liver injury. Therefore, investigators must report as an adverse event the occurrence of either of the following:

Treatment-emergent ALT or AST $> 3 \times$ baseline value in combination with total bilirubin $> 2 \times$ ULN (of which $\geq 35\%$ is direct bilirubin),

Treatment-emergent ALT or AST $> 3 \times$ baseline value in combination with clinical jaundice.

This abnormal laboratory values related to the liver function should be recorded on the Adverse Event eCRF and reported immediately as a SAE (AESI).

The severity will be classified according to the NCI CTCAE Version 5.0. The CTCAE is available for downloading on the internet (see appendix 1).

The AE severity grade provides a qualitative assessment of the extent or intensity of an AE, as determined by the investigator or as reported by the patients. The severity grade does not reflect the clinical seriousness of the event, only the degree or extent of the affliction or occurrence (e.g., severe nausea, mild seizure), and does not reflect the relationship to study drug.

Severity grade for other adverse events not covered in the toxicity grading scale:

| | |
|-------------|------------------|
| 1 = Grade 1 | Mild |
| 2 = Grade 2 | Moderate |
| 3 = Grade 3 | Severe |
| 4 = Grade 4 | Life-threatening |
| 5 = Grade 5 | Fatal |

However, depending on the SAE term used, there is some AE that do not have all the grades (e.g., the SAE term Alopecia only has the Grade 1 and 2).

The causal relationship to study drug is determined by the physician and should be used to assess all AE. The causal relationship can be one of the following:

Related: There is a reasonable causal relationship between study drug administration and the AE.

Not related: There is not a reasonable causal relationship between study drug administration and the AE.

The term "reasonable causal relationship" means there is evidence to suggest a causal relationship.

About the AEs that must be recorded in the eCRF note that:

- Baseline symptoms will be recorded on the eCRF and changes and updates in grade as well as resolution of an AE during treatment must be reported,
- An AE should be reported for each SAE notified,
- AEs should not be reported in a narrative description.

AEs can be spontaneously reported or elicited during open-ended questioning, examination, or evaluation of a subject (to prevent reporting bias, subjects should not be questioned regarding the specific occurrence of one or more AEs).

Any AE must be reported by an entry in the eCRF within 5 days of awareness, even if they do not meet the whole information. The diagnosis of the event should be recorded as AE term. If there is a secondary AE separated in time from the initiating event, it should be recorded as an independent event (e.g., if vomiting results in severe dehydration, both events should be reported separately).

13.2. Definition of Serious Adverse Event (SAE) and Suspected Unexpected Serious Adverse Reaction (SUSAR)

A Serious Adverse Event (SAE) is defined in general as any undesirable medical occurrence/adverse drug experience that occurs [REDACTED]

[REDACTED], regardless of whether it is considered related or not to the study drug and that, at any dose, results in any of the following:

- results in death (fatal)
- is life-threatening (defined as an event in which the participant was at risk of death at the time of the event; it does not refer to an event which hypothetically might have caused death if it was more severe)
- requires inpatient hospitalization or causes prolongation of existing hospitalization (see **NOTE 2** below)
- results in persistent or significant disability/incapacity
- is a congenital anomaly/birth defect
- is an important medical event. Defined as a medical event(s) that may not be immediately life-threatening or result in death or hospitalization but, based upon appropriate medical and scientific judgment, may jeopardize the subject or may require intervention (e.g., medical, surgical, laboratory abnormal parameters...) to prevent one of the other serious outcomes listed in the definition above (see **NOTE 3** below)

After informed consent has been obtained, but prior to initiation of study drug, only serious adverse events caused by a protocol-mandated intervention (e.g., invasive procedures such as biopsies, discontinuation of medications) should be reported.

Seriousness is based on patient/event outcome or action criteria usually associated with events that pose a threat to a patient's life or functioning. Seriousness (not severity) serves as a guide for defining regulatory reporting obligations

NOTE 2: The following hospitalizations are not considered SAEs:

- A visit to the emergency room or other hospital department < 24 hours, that does not result in admission, except if it is considered as an important medical event or life- threatening
- elective surgery which has been planned prior to signing consent

- routine health assessment requiring admission for baseline/trending of health status (e.g., routine colonoscopy)
- admissions as per protocol for a planned medical/surgical procedure
- admission for administration of anticancer therapy in the absence of any other SAEs
- admission encountered for another life circumstance that carries no bearing on health status and requires no medical/surgical intervention (e.g., lack of housing, economic inadequacy, caregiver respite, family circumstances, administrative reason)
- progression of disease. By convention, clinical events related to the primary cancer being studied or to the primary cancer progression are not to be reported as SAEs, even if they meet any of the seriousness criteria from the standard SAE definition, unless the event is more severe than expected and therefore the investigator considers that their clinical significance deserves reporting.

NOTE 3: Any laboratory abnormalities should be documented as a SAE if:

- Intensive treatment in an emergency room or at home for allergic bronchospasm is needed,
- Blood dyscrasias or convulsions that do not result in hospitalization,
- Any untoward event related, and unexpected, to the protocol procedures,
- The laboratory test result is clinically significant or meets the definition of a SAE,
- The laboratory abnormality required the participant to have study drug discontinued or interrupted,
- The laboratory abnormality required the subject to receive specific corrective therapy.

A SAE report should be completed for any event where doubt exists regarding its seriousness. Although overdose, pregnancy, AESI (e.g., potential drug-induced liver injury (DILI)), important medical event, and cancer (secondary malignancy) are not always serious by regulatory definition, these events must be handled as SAEs. If applicable, SAEs must be collected that relate to any later protocol-specified procedure (e.g., a follow-up skin biopsy).

If the investigator believes that a SAE is not related to study drug but is potentially related to the conditions of the study (such as withdrawal of previous therapy or a complication of a study procedure), the relationship should be specified in the narrative section of the SAE Report Form and an important medical event would be the seriousness.

All deaths that occur during the reporting period that are clearly the result of disease progression should not be reported as a SAE, but they should be collected as an AE. All deaths where it is not due to disease progression and deaths with an unknown cause should always be reported as a SAE.

Death should be considered as an outcome and not the event, the AE causing the death must be reported as the SAE term. The term "sudden death" should be used only for the occurrence of an abrupt and unexpected death due to presumed cardiac causes in a patient with or without preexisting heart disease, within 1 hour after the onset of acute symptoms or, in the case of an unwitnessed death, within 24 hours after the patient was last seen alive and stable. If the cause of death is unknown and cannot be ascertained at the time of reporting, "Death due to Unknown Cause" should be recorded on the Adverse Event eCRF. If the cause of death later becomes available (e.g., after autopsy), the event should be replaced by the established cause of death.

If the SAE is considered as related to the study drug by the Principal Investigator, it is a Serious Adverse Reaction. The SAR is assessed by the Fundación GECP (SLCG/GECP) to know if it is expected. A SAR that is not listed as a known toxicity of the investigational drug in the summary of product characteristics (Investigator Brochure or Data Sheet) will be considered as a Suspected Unexpected Serious Adverse Reaction (SUSAR). The sponsor will inform to the Principal Investigator that this SAE has been considered as a SUSAR. In Spain, Health authority (AEMPS: Agencia Española del Medicamento y Productos Sanitarios) will also be informed about all SUSARs via EudraVigilance. Also, the autonomous regions will be informed about all SUSARs according to the current Spanish clinical trial regulation.

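### NOTE 2 in section 13.2 keeps cancer-related events out of SAE reporting, with no exception for events the investigator also judges related to bintrafusp alfa

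*Combined protocol and SAP*

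**What the plan says.** Section 13.2 defines an SAE by outcome, "regardless of whether it is considered related or not to the study drug". NOTE 2 then lists what is not to count. It is headed as a list of hospitalizations, but its last bullet, on progression, goes further: "clinical events related to the primary cancer being studied or to the primary cancer progression are not to be reported as SAEs", and this holds "even if they meet any of the seriousness criteria from the standard SAE definition". The one way back in is "unless the event is more severe than expected and therefore the investigator considers that their clinical significance deserves reporting".

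The rules around it are these:

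- Section 13.1 has the physician judge every AE as related or not related to study drug, and asks for AEs in the eCRF within 5 days of awareness.
- Section 13.5 asks for the SAE form within 24 hours of awareness.
- Later in section 13.2, an SAE that the investigator considers drug-related becomes a serious adverse reaction, and the sponsor then assesses whether it is expected. A SUSAR can arise only from that step.
- Section 13.3 puts AESIs on a 24-hour clock even when they are not serious. Its list is redacted.
- NOTE 3 in section 13.2 makes certain laboratory abnormalities SAEs, for example when "The laboratory abnormality required the participant to have study drug discontinued or interrupted".

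**The concern.** NOTE 2 asks whether an event is cancer-related and, apart from severity, asks nothing more. It does not ask whether the drug may also have contributed. The two attributions are not exclusive: the causality scale in 13.1 concerns the drug alone, and nothing there prevents a physician from marking an event as drug-related while also seeing the tumour as a cause. For such an event, the rule for recognising drug reactions is never reached, because NOTE 2 has already removed SAE status.

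What is at stake is the sponsor's safety oversight. This is a single-arm trial of 47 patients with no control group to help separate drug effects from disease effects. Under section 19.5 the IDMC relies on the sponsor's staff to bring issues to it. An event that an investigator has marked as drug-related, and that meets a seriousness criterion, is one the sponsor should see quickly and check for expectedness.

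**Working it through.** No statistical figure is involved. The check sets the rules side by side and compares two reporting limits.

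**Inputs**

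- AE entry: 5 days (13.1).
- SAE form: 24 hours (13.5).
- AESI report: 24 hours (13.3).
- Scope and exception of the cancer convention: 13.2, NOTE 2.
- Start of the serious adverse reaction and SUSAR step: an event already classed as an SAE and considered drug-related (13.2).

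**Route of a non-fatal event that meets a seriousness criterion**

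| Investigator's judgment | NOTE 2 applies? | Reporting limit | Expectedness assessed? |
|---|---|---|---|
| Drug-related, not cancer-related | No | 24 h | Yes |
| Cancer-related, not drug-related | Yes | 5 days | No, and it would not be in any case |
| Both | Yes, as written | 5 days | No |
| Both, and on the AESI list | 13.3 gives its own route | 24 h | Not stated for an event that NOTE 2 also covers |
| Both, unexpectedly severe and considered worth reporting | Exception used | 24 h | Yes |

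The third row is the gap. Compared with the first, the drug attribution and the seriousness are the same. Only the added cancer attribution differs, and it removes both the 24-hour report and the expectedness assessment. The second row shows that the SUSAR step is not lost for events judged unrelated to the drug, since they would never enter it.

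**Size of the delay**

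5 days × 24 h = 120 h. 120 h − 24 h = 96 h = 4 days. This is the largest difference between the two limits, not an expected delay. For an event that the AESI rule already puts on 24 hours, it is 24 h − 24 h = 0.

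**Do the other rules in 13.2 close the third row?**

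- The exception in NOTE 2 is a test of severity. A suspected drug contribution does not trigger it.
- NOTE 3 has a trigger for drug interruption, but it is worded for laboratory abnormalities. It may capture a haemoglobin fall, for example, but not the clinical event behind it.
- The sentence on doubt concerns doubt about seriousness, not about cause.
- A further sentence says that "important medical event, and cancer (secondary malignancy) are not always serious by regulatory definition, these events must be handled as SAEs". This points towards reporting, but the protocol does not say whether it or NOTE 2 prevails for a cancer-related event.

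Each of these can catch some events; none is a rule for drug-related events as such.

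**The case against.** The strongest reply is that the gap is narrow and existing routes cover much of it. NOTE 2 hangs on the hospitalization criterion and opens with disease progression, so a site may well read it as covering plain progression only. An event serious enough to matter will often be unexpectedly severe, come with a laboratory abnormality under NOTE 3, or fall under an AESI; treatment-related anaemia is one of those named in section 3.3. Fatal events follow a separate rule: a death not due to progression, or of unknown cause, is always an SAE. All of this stands and limits how often the gap would matter. It does not remove it, because the bullet expressly covers every seriousness criterion and none of these routes turns on drug relation.

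A reader might go further and infer that serious tumour bleeding in this trial escapes 24-hour reporting. Section 11.2 says of tumour bleeding at Grade 2 or above that "Study treatment must be held till the event recovers to Grade" 1 or lower, and it halves the dose on resumption after a Grade 3 or higher "bleeding event had been observed, regardless of causality with the study intervention". The documents do not support that inference:

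- The AESI list in 13.3 is redacted and may include tumour bleeding. The readable list in 3.3 names four types, none of them bleeding, but it is not complete: sections 13.1 and 13.2 also treat liver injury as an AESI.
- The bleeding risk stated for the drug in 3.3 is mucosal bleeding. It has its own table in 11.2 and, not being cancer-related, is not what NOTE 2 addresses.
- For a clinical event, a hold or dose cut is not a seriousness criterion in 13.2. The actions in 11.2 therefore do not show that a bleed was misclassified, and there is no contradiction with NOTE 3, which concerns laboratory findings.

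Tumour bleeding is thus an illustration of where the question could arise, not evidence that it does.

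**Conclusion.** The point holds for one class of event: non-fatal, meeting a seriousness criterion, judged both cancer-related and drug-related, not on the AESI list, and not caught by the severity exception or NOTE 3. For that class the text as written allows a report up to 96 hours later than the SAE limit and requires no expectedness assessment, so a SUSAR could go unrecognised.

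This rests on reading NOTE 2 literally and on the readable text of 13.2 and 13.3, parts of which are redacted. It also assumes that the event is still entered as an AE. Section 13.1 leaves out events that clearly fit expected progression, and an event marked as drug-related should not normally be one of those. The number of patients affected cannot be estimated from the documents.

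Nothing here touches the patient's own treatment, the PFS analysis or the decision rule, and the event would normally remain in the AE data that serve the safety objective. The change is a cheap improvement, not a correction on which the trial's conclusions depend.

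**What to change.** Add one sentence to the last bullet of NOTE 2 in section 13.2: *This convention does not apply to any event the investigator considers related to study drug ('Related' in 13.1), or to any AESI in 13.3; such events are reported within 24 hours under 13.5.*

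The first part restores the expectedness assessment for drug-related serious events. The second makes clear that 13.3 takes precedence over NOTE 2, and it settles tumour bleeding if the redacted list includes it. If the list does not, the sponsor can decide separately whether to add it.

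The cost is one sentence in an amendment and a few extra SAE reports for events that turn out to be due to the cancer. The convention for plain progression stays as it is, and sections 11.2 and 16 need no change.
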